## 11.6 Excessive Toxicity – Criteria for Stopping and Interim Safety Analysis

In case of excessive toxicity, safety-stopping rules will be used. An acceptable toxicity rate will be assumed at 0.20. The study will be stopped based on an unacceptable excessive toxicity rate of 0.40. A sequential probability ratio test will be used where a likelihood ratio of 8 in favor of an excessive toxicity rate of 0.40 (vs. 0.20) provides sufficient evidence to stop the study due to excessive toxicity. Data will be continuously reviewed for excessive toxicity and statistical analysis performed if excessive toxicity is suspected. The table below provides the minimum number of patients exhibiting excessive toxicity that will trigger statistical analysis.

Total number of treated patients	Number of Patients observed with excessive toxicity
3	≥2
4-5	≥3
6-7	≥4
8-9	≥5
10-11	≥6
12-13	≥7
14-16	≥8
17-18	≥9
19-20	≥10

Version Date: 13AUG2018 Confidential Page 41 of 51

21-23	≥11
24-25	≥12
26-28	≥13
29-30	≥14
31-33	≥15
34-35	≥16
36-38	≥17
39-40	≥18

Ramucirumab will be held for drug related adverse events Grade  $\geq 3$  until recovery to Grade  $\leq 1$  and then resumed with a lower dose level -1 (6 mg/kg). If the Grade  $\geq 3$  related adverse event does not resolve within 4 weeks of holding treatment, the subject will be taken off study treatment.

In the case of prolonged or medically concerning Grade 2 toxicity related to the chemotherapy combination, treatment will be interrupted until recovery to Grade  $\leq 1$ , at which time treatment will be resumed at the same dose. If the adverse event does not resolve in or within 2 weeks with medical intervention, then the subject will be taken off study treatment.

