	recovery to grade ≤ 1, at which time treatment will be resumed at the same dose. If the adverse event does not resolve in or within 2 weeks with medical intervention, then the subject will be taken off trial.  In case of excessive toxicity, safety-stopping rules will be used. An acceptable toxicity rate will be assumed at 0.20. The study will be stopped based on an unacceptable excessive toxicity rate of 0.40. A sequential probability ratio test will be used where a likelihood ratio of 8 in favor of an excessive toxicity rate of 0.40 (vs. 0.20) provides sufficient evidence to stop the study due to excessive toxicity. Toxicity will be continuously reviewed for excessive toxicity and statistical analysis performed if excessive toxicity is suspected.  In the interim safety analysis, the study will be closed to accrual after the first 20 subjects (10 in each arm) are analyzed, if within the first cycle of treatment n/10 subjects developed any of the following grade ≥ 3 toxicity: 2/10 febrile neutropenia, 3/10 neuropathy, 3/10 hypertensive emergency or urgency, 3/10 life threatening thromboembolic event, 2/10 GI perforation or 2/10 bleeding or hemorrhage, the regimen mFOLFIRINOX RAM will be considered toxic and the trial will stop.
TOTAL NUMBER OF SUBJECTS	N = 85 to 95
ESTIMATED ENROLLMENT PERIOD	Estimated 24 months
ESTIMATED STUDY DURATION	Estimated 33 months

Page 8 of 51

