## 11.6.1 Excessive Toxicity

Excessive toxicity is defined as any adverse event that meets the following criteria:

- Any grade 3 or higher adverse event or an adverse event that leads to discontinuation of study therapy.
- The adverse event must be possibly, probably or definitely related to any of the study treatments (Ramucirumab, Oxaliplatin, Irinotecan, 5-FU)
- The adverse event occurs in the first four weeks of treatment
- The adverse event grade does not diminish to grade 1, four weeks after dose modification or dose delay. AE must have been adequately treated (e.g. nausea, vomiting, hematologic toxicities)

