## 11.6.2 Interim Safety Analysis

The study will be closed to accrual and an interim safety analysis conducted after ten subjects are accrued to each arm. If the following rates of selected toxicities listed below are observed within the first cycle of treatment (four weeks), the regimen (Ramucirumab, Oxaliplatin, Irinotecan, 5-FU) will be considered toxic and the trial will be stopped.

Adverse Event (≥ grade 3)	Toxicity Rate (n/10 subjects)
Febrile Neutropenia	2/10
Peripheral Motor or Sensory Neuropathy	3/10
Hypertension	3/10
Life Threatening Thromboembolic Event	3/10
GI Perforation	2/10
Hemorrhage, Bleeding	2/10

Version Date: 13AUG2018 Confidential Page 42 of 51

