## 11.10 Sample Size/Accrual/Study Duration

We aim to test the null hypothesis of PFS at 6 months. Using a one-sided log-rank test we have estimated a sample size of 85 patients (43 in one and 42 in another arm) which will provide 80% power under a type 1 error of 20%. This is an estimation on 24 months accrual and 9 months follow up after accrual for the primary endpoint. Sample size may increase to 95 to account for a 10% drop out rate.

The expected progression free survival for mFOLFIRINOX in metastatic pancreatic cancer is 6 months. The addition of RAM to mFOLFIRINOX would be expected to increase the median PFS to at least 9 months. We assume a type 1 error ( $\alpha$ ) of 0.2 and a power (1- $\beta$ ) of 80%.

With an exact power of 0.8014, hazard ratio of 0.6667 and endpoint of detecting 3 months PFS advantage of the mFOLFIRINOX/ramucirumab combination over mFOLFIRINOX alone (from 6 to 9 months), the sample size on each arm was calculated to be 43 in the control arm and 42 in the treatment arm (total is 85). 29.30

The estimated enrollment period for this study is 24 months and the estimated study duration is 33 months.

Version Date: 13AUG2018 Confidential Page 43 of 51

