## 12. TRIAL MANAGEMENT

# 12.1 Data and Safety Monitoring Plan

The study will be conducted in accord with the Winship Cancer Institute of Emory University's Data and Safety Monitoring Plan (DSMP).

In addition, HCRN data and safety activities include:

- Review all adverse events requiring expedited reporting as defined in the protocol
- Notify participating sites of adverse events requiring expedited reporting
- Provide data summary reports to the sponsor-investigator on a monthly basis
- Submit data summary reports to the lead institution Data Safety Monitoring Committee for review as per their guidelines.

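### From 12 treated patients onward, the section 11.6 toxicity trigger table sits 1 to 4 events above the likelihood-ratio rule it should serve

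*Combined protocol and SAP*

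**What the plan says.** Section 11.6 takes 0.20 as the acceptable toxicity rate and 0.40 as the unacceptable one, and sets a sequential probability ratio test: "a likelihood ratio of 8 in favor of an excessive toxicity rate of 0.40 (vs. 0.20) provides sufficient evidence to stop the study". On timing it says "Data will be continuously reviewed for excessive toxicity and statistical analysis performed if excessive toxicity is suspected". It introduces the table with "The table below provides the minimum number of patients exhibiting excessive toxicity that will trigger statistical analysis". The counts run from 2 or more at n = 3, through 7 at n = 12–13, 10 at n = 19–20 and 14 at n = 29–30, to 18 at n = 39–40.

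The synopsis gives the same LR rule without the table and also says "The study will be stopped based on an unacceptable excessive toxicity rate of 0.40". No other rates, prior or cut-off is given from which the counts could have been derived.

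**The concern.** A count that prompts an analysis should be at or below the count at which that analysis would stop the trial. If it is above, staff who rely on the table are not prompted until the evidence has already passed the protocol's own standard. The table is the only numerical prompt for the LR test, so the error bears on how reliably the trial stops when the regimen is as toxic as the plan calls unacceptable.

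**Working it through.** **Inputs (section 11.6).** Rates 0.20 and 0.40, LR threshold 8, and the printed counts for n = 3 to 40.

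**Boundary implied by the rule.** With x events in n patients,

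LR(n, x) = (0.40/0.20)^x × (0.60/0.80)^(n−x) = 2^x × 0.75^(n−x).

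LR ≥ 8 requires x ≥ [ln 8 + n ln(4/3)] / [ln 2 + ln(4/3)] = 2.120 + 0.2933n.

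**Comparison with the printed table.**

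| Printed minus LR boundary | Sample sizes | Number of sizes |
|---|---|---|
| −1 | 3, 4, 5, 7 | 4 |
| 0 | 6, 8–11 | 5 |
| +1 | 12–18 | 7 |
| +2 | 19–25, 27, 28 | 9 |
| +3 | 26, 29–35, 38 | 9 |
| +4 | 36, 37, 39, 40 | 4 |

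Examples (printed against LR boundary): n = 20, 10 against 8; n = 30, 14 against 11; n = 40, 18 against 14.

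At every n from 12 to 40, one event below the printed count already has LR above 8. The smallest such value is 2^6 × 0.75^7 = 8.5 at 6/13 and the largest is 234 at 17/39. At the printed count itself the LR runs from 22.8 (7/13) to 623 (18/39).

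**A check that does not depend on how the trial is run.** The lowest observed rate that the table flags at any size is 17/38 = 44.7%. An observed rate of exactly 40% therefore never triggers it, although 8/20, 12/30 and 16/40 have LR 8.1, 23.1 and 65.8.

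**Could another threshold explain the table?** No. The printed counts rise from 2 to 18 between n = 3 and n = 40, which is 16/37 = 0.43 events per patient. Any LR boundary at 0.20 vs 0.40 rises by 0.293. No threshold from 1 to about 3,000 at these rates matches more than 10 of the 38 sizes.

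**Effect on stopping.** Exact forward recursion, with a look after every patient from n = 3 to 40, independent outcomes, one count and immediate ascertainment. Section 11.6 does not say how the table and the rule combine, so four readings are shown.

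| Reading | True rate 0.40: stop by n = 20 | by n = 30 | by n = 40 | True rate 0.20: stop by n = 40 |
|---|---|---|---|---|
| LR ≥ 8 checked after every patient | 64.7% | 78.5% | 86.6% | 8.5% |
| LR computed only when the table count is met | 44.1% | 51.5% | 56.7% | 3.8% |
| LR checked after every patient once the table has first triggered | 50.3% | 58.5% | 63.8% | 5.0% |
| Table itself is the stopping boundary | 56.7% | 62.0% | 65.8% | 13.2% |

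By n = 11 the first three readings all stop 34.0% of trials at a rate of 0.40, so the table costs nothing up to that point.

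**Where the loss arises at a true rate of 0.40.** LR ≥ 8 is first met at n = 12 or later in 86.6 − 34.0 = 52.6% of trials. In 14.3% the table had already flagged the trial, at n = 3, 4, 5 or 7. In the other 38.3% it had not yet called for any analysis: it does so later by n = 40 in 15.5%, and never in 22.8%.

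**Ascertainment lag.** Section 11.6.1 counts an event from the first four weeks of treatment only if "The adverse event grade does not diminish to grade 1, four weeks after dose modification or dose delay", so confirmation can take about eight weeks. Section 11.10 states "The estimated enrollment period for this study is 24 months and the estimated study duration is 33 months". At 85 subjects in 24 months, about 85/24 × (56/30.4) = 6.5 more subjects would enrol meanwhile. The stopping percentages are therefore idealised under every reading.

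**The case against.** The best defence is that the table changes no stopping standard. LR 8 remains the criterion, the table only marks where an analysis becomes mandatory, and the continuous-review sentence allows an earlier one on suspicion. If the LR is in fact computed after every patient, nothing is lost. This stands as a statement of what is permitted. But the suspicion sentence sets no count, and a mandatory prompt above the stopping threshold is misplaced as a backstop.

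The lateness is also row by row rather than true of every trial. At a rate of 0.40 the table has prompted analysis at or before the LR crossing in 34.0 + 14.3 = 48.3% of trials. That is correct; the late or absent prompt concerns the other 38.3%.

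The 40% check has limits at small n, because the LR rule does not flag 4/10 (LR 2.8) or 6/15 (LR 4.8) either. It tells the two apart only from about n = 20.

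Other safeguards exist. Section 11.6.2 says "The study will be closed to accrual and an interim safety analysis conducted after ten subjects are accrued to each arm", with limits for six named toxicities. Section 12.1 has the coordinating organisation "Provide data summary reports to the sponsor-investigator on a monthly basis", and section 12.2 adds a yearly committee review of aggregate adverse events. These mitigate, but none applies the LR rule.

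Finally, the documents never say that the table was derived from LR ≥ 8. That leaves open how the discrepancy arose; it does not make the two parts of section 11.6 agree.

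**Conclusion.** The mismatch is confirmed and should be corrected before the rule is relied on. It is exact and rests only on the two rates, the threshold and the printed counts: 1 to 4 events too high at all 29 sizes from n = 12 to 40. Up to n = 11 the table delays nothing.

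The practical loss depends on conduct that the documents leave open. At a true rate of 0.40, stopping by n = 40 falls from 86.6% to between 56.7% and 65.8% wherever the table governs, and does not fall if the LR is computed after every patient regardless. In that last case the table has no function, so no reading makes the printed counts agree with the stated rule. Used as a boundary, the table is also worse at the acceptable rate of 0.20 (13.2% against 8.5%), because of its lower entries at n = 3, 4, 5 and 7.

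**What to change.** Reconcile the table with the rule in one of two ways.

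1. Regenerate it from LR ≥ 8 for 0.40 vs 0.20:

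| Treated | Minimum events |
|---|---|
| 3 | 3 |
| 4–6 | 4 |
| 7–9 | 5 |
| 10–13 | 6 |
| 14–16 | 7 |
| 17–20 | 8 |
| 21–23 | 9 |
| 24–26 | 10 |
| 27–30 | 11 |
| 31–33 | 12 |
| 34–37 | 13 |
| 38–40 | 14 |

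   This removes the early prompts at 2/3, 3/4, 3/5 and 4/7. No stop is lost, because the LR there is only 3.0, 6.0, 4.5 and 6.75. If the table is to remain a prompt rather than a boundary, those four lower entries can stay.

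2. Or keep the printed counts, state the rates and likelihood ratio that they represent, and give their stopping probabilities at 0.20 and 0.40.

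It would also help to say whether counts are per arm or pooled, and what applies after n = 40. These are clarifications, not errors.

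The cost is one table replaced or relabelled, with no extra patients or data. It does need a protocol amendment, with the approvals listed in section 13.5 (sponsor-investigator, drug supplier and each site's IRB).

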#### 11. STATISTICAL METHODS

## 11.1 Study Design

This is a phase II, multicenter, double-blinded, randomized, 2-arm trial evaluating the efficacy and safety of mFOLFIRINOX + RAM (Arm A) vs. mFOLFIRINOX + placebo (Arm B) in 85 subjects with advanced PCA, not amenable to curative treatment. Subjects will be randomized in a 1:1 ratio (i.e., there will be 43 subjects in the control group and 42 subjects in the treatment group). The primary objective of this trial is to estimate and compare PFS in Arm A versus Arm B. See section 11.10 for a description of the power/sample size analysis based on the logrank test.

Version Date: 13AUG2018 Confidential Page 40 of 51

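### The section 11.6 toxicity trigger table stops at 40 treated patients in a trial of 85 to 95, so the stopping rule has no tabulated trigger for the last 45 to 55 patients

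*Combined protocol and SAP*

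**What the plan says.** Section 11.6 sets two toxicity rates and a criterion: "An acceptable toxicity rate will be assumed at 0.20"; "The study will be stopped based on an unacceptable excessive toxicity rate of 0.40"; and, under a sequential probability ratio test, "a likelihood ratio of 8 in favor of an excessive toxicity rate of 0.40 (vs. 0.20) provides sufficient evidence to stop the study". On when the ratio is to be examined it says: "Data will be continuously reviewed for excessive toxicity and statistical analysis performed if excessive toxicity is suspected". It then introduces a table: "The table below provides the minimum number of patients exhibiting excessive toxicity that will trigger statistical analysis". The first column is headed "Total number of treated patients". The rows run from 3 patients (2 or more with excessive toxicity) to 39-40 patients (18 or more).

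Section 11.1 plans the trial "in 85 subjects with advanced PCA, not amenable to curative treatment". Section 11.10 adds: "Sample size may increase to 95 to account for a 10% drop out rate". The synopsis gives the same range and repeats the likelihood-ratio rule, without the table.

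No sentence says that toxicity monitoring ends at 40 patients, and no row or sentence gives a trigger count beyond 40.

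**The concern.** The table turns a promise of continuous review into something that can be carried out: at so many treated patients, this many toxicities means the ratio is computed. It goes silent before half of the planned patients have been treated. After that, the remaining prompt is that excessive toxicity is suspected. Section 11.6.1 defines the events to be counted, but nothing defines how many of them amount to suspicion.

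The other numeric safety rule, in section 11.6.2, is a single look after ten subjects per arm, so it does not cover the later patients. If the regimen is as toxic as the rate the plan calls unacceptable, the evidence may reach the stopping standard only after patient 40. No tabulated count would then send anyone to check.

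**Working it through.** **Inputs.** Section 11.6: acceptable rate 0.20, unacceptable rate 0.40, likelihood ratio 8, and the printed counts for n = 3 to 40. Sections 11.1 and 11.10: 85 subjects (43 and 42), up to 95.

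**1. Reproducing the printed table.** With x toxicities in n patients,

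LR = (0.40/0.20)^x × (0.60/0.80)^(n−x) = 2^x × 0.75^(n−x).

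The boundary is the smallest x with LR ≥ 8, that is, x ≥ [ln 8 + n ln(4/3)] / ln(8/3).

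The printed counts do not follow from this. They agree at 5 of the 38 values of n (6, 8, 9, 10 and 11). At n = 3, 4, 5 and 7 the table triggers at ratios of only 3.0 to 6.75. From n = 12 it asks for more events than a ratio of 8 needs:

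| n | printed count | LR at printed count | smallest count with LR ≥ 8 |
|---|---|---|---|
| 20 | 10 | 58 | 8 |
| 30 | 14 | 164 | 11 |
| 40 | 18 | 468 | 14 |

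Other likelihood-ratio parameters, Beta posterior rules and binomial tail rules were tried. None reproduced the whole table; the best matched 35 of 38.

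**2. Coverage.** 85 − 40 = 45 patients (45/85 = 53%) and 95 − 40 = 55 patients (55/95 = 58%) lie beyond the last row.

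**3. The stated rule beyond 40.** The formula has no upper limit on n. It gives 15 at 41-43, 20 at 58-60, 28 at 85-88 and 30 at 92-95. Checks: at n = 85, 27 events give LR = 7.6 and 28 give 20.3; at n = 95, 30 events give 8.1.

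**4. Probability of a trigger.** This is an exact forward recursion over the binomial path, absorbing at the first crossing. Patients are counted one at a time and outcomes are taken as known at once.

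| True rate, all treated patients | Printed table (ends at 40) | LR ≥ 8 to 40 | LR ≥ 8 to 85 | LR ≥ 8 to 95 |
|---|---|---|---|---|
| 0.40 | 0.658 | 0.866 | 0.977 | 0.985 |
| 0.20 | 0.132 | 0.085 | 0.096 | 0.096 |

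At 0.40 the shortfall of the printed table against the stated rule at 85 is 0.977 − 0.658 = 0.319. Under the stated rule throughout, stopping at 40 costs 0.977 − 0.866 = 0.111; the other 0.866 − 0.658 = 0.208 comes from the printed counts differing from the rule.

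The plan gives no arm-specific rates. As an illustration, assume 0.40 in Arm A and 0.20 in Arm B, pooled and alternating with Arm A first. The printed table then triggers with probability 0.36, and LR ≥ 8 gives 0.46 at 40, 0.62 at 85 and 0.65 at 95.

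**5. Per-arm reading.** If the count were per arm (42-43, up to 48 with dropout), LR ≥ 8 at a true rate of 0.40 gives 0.866 at 40, 0.871 at 42 and 0.901 at 48. The loss from the table's range is 0.5 to 3.5 points.

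**6. Appending rows to the printed table.** The trigger would fall from 18 at n = 40 to 15 at n = 41. At a true rate of 0.40 the cumulative trigger probability would jump from 0.658 to 0.812 with that one patient. At 0.20 the false-trigger chance would rise from 0.132 to 0.151 at n = 85.

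**The case against.** A reader might infer that toxicity monitoring ends at patient 40, or that nothing thereafter could lead to a stop. The documents do not support that. The stopping criterion is the likelihood ratio of 8, which has no upper n and stands in the synopsis without any table. Section 11.6 also calls for analysis whenever excessive toxicity is suspected. Section 12.1 provides monthly data summaries to the sponsor-investigator and reports to the monitoring committee, and section 12.2 provides annual committee review of aggregate adverse events. These are real occasions for someone to act. This part of the objection stands: the rule survives, and only its pre-computed trigger lapses. None of these reviews supplies a number, however, so the gap in the table remains.

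It can also be said that the table may be meant per arm, in which case it nearly reaches the end of each arm. The column heading refers to the total of treated patients and nothing in the section mentions arms, so the pooled reading is the natural one. If per arm was intended, the range defect is minor, and the heading needs correcting instead.

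Finally, one might quote only the 11-point loss from stopping LR ≥ 8 at 40 patients. That describes a table faithful to the stated rule, which the printed table is not.

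**Conclusion.** The point holds as a defect in the range of the table. Read as headed, the table gives no trigger count for the last 45 to 55 patients, although review is meant to be continuous and the criterion itself continues to apply.

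If the printed table is the only numeric prompt, a true rate of 0.40 in all treated patients goes untriggered about 34% of the time (1 − 0.658). Under the stated rule carried to 85 patients that figure is about 2% (1 − 0.977). Both the early end of the table and the mismatch of its counts with the stated rule contribute to this difference.

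The figures assume a pooled count, a common rate in both arms and outcomes known at once. They give the chance of a numeric prompt, not the chance that the trial would be stopped, since the reviews in sections 11.6, 12.1 and 12.2 could lead to an analysis without one. The change should be made, but the plan is not without a toxicity rule after patient 40.

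**What to change.** Replace the section 11.6 table; do not extend it. Generate every row from the stated rule, the smallest x with 2^x × 0.75^(n−x) ≥ 8, through the largest planned number: 95 if all treated patients are counted, 48 if the count is per arm. Example rows are 8 at n = 20, 11 at 30, 14 at 40, 15 at 41-43, 20 at 58-60, 28 at 85-88 and 30 at 92-95. If the printed counts came from a different rule that the sponsor means to keep, the text should state that rule and the table should be carried on from it, so that one rule governs throughout.

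Name the denominator, either all treated patients as now headed or patients per arm. State that review continues until the last treated patient has completed the toxicity window.

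The cost is one revised table, with no new data or patients. At the acceptable rate of 0.20 the false-trigger chance is about 10% (0.096). That is about 1 point more than the same rule stopped at 40 (0.085), and lower than with the printed table (0.132).

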#### 4.1 Blinding

Site pharmacy staff and HCRN EDC administrative team will be unblinded to the study treatment. Subjects, site investigators, site analysis teams, and other site personnel will be blinded to the study treatment.

Unblinding of site personnel may occur for emergency purposes only. Site investigators should note that the occurrence of a serious adverse event or progressive disease should not routinely precipitate the immediate unblinding of the label. The site investigator will contact HCRN to unblind a subject. If this is not feasible, HCRN must be notified **within 24 hours** of unblinding.

In compliance with applicable regulations, in the event of a serious adverse event (SAE), the subject's treatment assignment may be unblinded before reporting to the health authorities, ethic committees, and site investigators if the SAE was related (possibly, probably, definitely) to the blinded treatment.

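### The continuous toxicity rule in section 11.6 does not name the arm it counts; if both arms are pooled, it is clearly less likely to stop for excess toxicity on ramucirumab

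*Combined protocol and SAP*

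**What the plan says.** Section 11.6 fixes two rates: "An acceptable toxicity rate will be assumed at 0.20", and "The study will be stopped based on an unacceptable excessive toxicity rate of 0.40". The evidence needed to stop is "a likelihood ratio of 8 in favor of an excessive toxicity rate of 0.40 (vs. 0.20"). A table of limits, running from 3 to 40 patients, is headed "Total number of treated patients". Its role is limited: "The table below provides the minimum number of patients exhibiting excessive toxicity that will trigger statistical analysis". The stop itself rests on the likelihood ratio. The synopsis repeats the two rates and the ratio without the table. Neither place names an arm.

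Under section 11.6.1 an event counts if it is possibly, probably or definitely "related to any of the study treatments (Ramucirumab, Oxaliplatin, Irinotecan, 5-FU"), so a chemotherapy toxicity in a placebo patient can qualify. Section 4.1 limits unblinding: "Site pharmacy staff and HCRN EDC administrative team will be unblinded to the study treatment". Section 11.8 only refers back to 4.1. Section 12.2 has the Data and Safety Monitoring Committee (DSMC) look at aggregate adverse event data once a year.

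Section 11.6.2 adds a separate "interim safety analysis conducted after ten subjects are accrued to each arm", with limits out of 10 for six named toxicities. The synopsis ties those limits to the ramucirumab regimen. Section 11.1 plans 1:1 randomization with 42 patients on ramucirumab and 43 on control.

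**The concern.** The safety question is whether ramucirumab added to mFOLFIRINOX is too toxic. A one-group test answers it only if the group is the patients given the combination. If placebo patients enter the numerator and denominator, and their rate is lower, they pull the observed rate towards the acceptable value, and a true excess on ramucirumab is less likely to reach the limit.

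This is the only continuous toxicity rule in the plan. After the single look at 10 per arm, and for any toxicity outside the six named there, it is the only formal rule left. As written, two competent analysts could apply it to different populations and reach different decisions from the same data.

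**Working it through.** **Inputs from the plan.** Rates 0.20 and 0.40, likelihood ratio (LR) 8, table from 3 to 40 patients (section 11.6); 1:1 allocation, 42 on ramucirumab, 85 in all (section 11.1).

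**Assumptions.** Arm A truly at 0.40. Arm B at 0.20, the plan's acceptable rate, with range 0.10 to 0.30, because no Arm B rate is given. The rule is checked after every patient. Arms arrive in random order, so a pooled patient's event probability is the mean of the two rates.

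**Step 1: try to reproduce the printed table.** For x events in n patients,

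LR = (0.40/0.20)^x × (0.60/0.80)^(n−x) = 2^x × 0.75^(n−x).

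The limit is the smallest x with LR ≥ 8.

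- n = 3: the table prints 2, where LR = 2² × 0.75 = 3.0, short of 8.
- n = 20: 7 events give 2^7 × 0.75^13 = 3.04 and 8 give 2^8 × 0.75^12 = 8.11, so the limit is 8. The table prints 10, where LR = 57.7.
- n = 40: 13 events give 2^13 × 0.75^27 = 3.47 and 14 give 2^14 × 0.75^26 = 9.25, so the limit is 14. The table prints 18, where LR is about 468.

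Over the 38 sample sizes from 3 to 40 the table agrees with LR ≥ 8 at five (6, 8, 9, 10 and 11). It is looser at 3, 4, 5 and 7, and stricter at every size from 12 on. The plan's own figures do not reproduce.

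**Step 2: the effect of pooling.** With Arm A at 0.40 and Arm B at 0.20 the pooled rate is (0.40 + 0.20)/2 = 0.30. The mean change in log LR per patient is p × ln 2 + (1 − p) × ln 0.75:

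- p = 0.40: +0.105
- p = 0.30: +0.007
- p = 0.20: −0.092

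Pooling removes most of the upward drift, though chance variation still carries many trials over the limit.

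**Step 3: probability of reaching LR ≥ 8**, by exact patient-by-patient binomial recursion with Arm A at 0.40:

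| Counted | When 40 are treated (20 in Arm A) | Whole trial (85; 42 in Arm A) |
|---|---|---|
| Arm A alone | 65% | 87% |
| Pooled, Arm B 0.10 | 23% | 30% |
| Pooled, Arm B 0.20 | 46% | 62% |
| Pooled, Arm B 0.30 | 69% | 87% |

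Strict alternation starting with Arm A lowers the 0.10 row to about 21.5% and 28%. With Arm B at 0.20, pooling costs 65 − 46 = 19 points when 40 are treated and 87 − 62 = 25 points over the whole trial. With both arms at 0.20 the pooled rule stops falsely in 8.5% of trials by 40 and about 9.5% by 85; Arm A alone, over 42 patients, does so in 8.5%. Pooling therefore does not buy a lower false-stop rate.

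**Step 4: the printed limits instead of LR ≥ 8.** Pooled to 40 with 0.40 and 0.20, the table is crossed in 33% of trials in random order (36% if arms alternate with Arm A first, 28% with Arm B first). On Arm A alone at 0.40 it is crossed in 66% by 40 Arm A patients, against 87% for LR ≥ 8; at a true 0.20 it is crossed in 13%, against 8.5%. If a stop needs both a table crossing and LR ≥ 8, the probabilities at 40 patients fall to 20% (pooled) and 57% (Arm A alone).

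**The case against.** The strongest reply is that the plan never says the arms are pooled. Three features favour an Arm A reading. The table ends at 40, close to the 42 planned for ramucirumab and far from 85. The drugs listed in section 11.6.1 are those that section 11.6.2 calls the regimen, which the synopsis names as mFOLFIRINOX with ramucirumab. And blinding does not force pooling, since the look at 10 per arm needs by-arm counts under the same blinding. This stands: pooling is the literal reading, not an established fact. It does not remove the need for a correction, because either intention requires the arm to be written down.

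It is also fair that the table only triggers an analysis and that section 11.6.2 offers protection of its own. The first point helps little, because a pooled likelihood ratio is diluted too. The second is a partial safeguard: one look, six named toxicities, first cycle only.

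A reader might infer more than the documents support:

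- That the rule misses a fixed share, such as half, of the cases it should stop. The share depends on the unknown Arm B rate, the boundary used and the number treated.
- That pooling cuts the stopping probability from 87% to 46%. That sets a whole trial against less than half of one; the like-for-like pairs are 65% against 46% and 87% against 62%.
- That a pooled rule cannot tell the two rates apart. It stops 62% of trials in the mixed case, against about 9.5% when both arms are at 0.20.
- That counting Arm A alone would separate ramucirumab toxicity from backbone toxicity. No one-group test does that; it takes the Arm B counts beside it.

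**Conclusion.** The point holds as an unspecified counting population with a material consequence, not as proof that the arms are pooled. If they are, and Arm B is at the assumed 0.20, the chance of stopping for a true Arm A rate of 0.40 falls by 19 points when 40 are treated and by 25 points over the whole trial. If Arm B is at 0.30, the loss over the whole trial vanishes (87% either way); at 0.10 the pooled rule stops in only about 28% to 30%. These figures assume a check after every patient and take no credit for section 11.6.2.

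A second defect needs no assumption about pooling: the printed limits do not follow from the stated likelihood ratio of 8. Relabelling the column would therefore not be enough, since the existing limits on Arm A alone are crossed in only 66% by 40 patients at a true rate of 0.40.

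**What to change.** 1. In section 11.6 and the synopsis, state that the likelihood-ratio rule is applied to Arm A patients, and relabel the table column accordingly. Tabulate Arm B counts beside it.
2. Recompute the limits from the stated ratio of 8 and extend them to all planned Arm A patients. If the printed limits were intended, state the rule that produced them and reconcile it with the ratio. Say whether a stop needs the ratio alone or also a table crossing.
3. Report operating characteristics: the probability of stopping at true rates of 0.20, 0.30 and 0.40, with the number treated.
4. State who produces the count. The HCRN electronic data capture team is already unblinded and can send by-arm counts to the DSMC only, so that sites and the sponsor-investigator stay blinded. The timing must match the continuous review in section 11.6, which an annual aggregate report does not.

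The cost is wording in section 11.6, the synopsis and the DSMC report, plus one recalculated table. No patients or procedures are added. The small downside is that the DSMC sees counts by arm.
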